1. Education on palliative care 2. Self-care for the caregiver a. Balancing family, self, and caregiving responsibilities b. Sleep and rest c. Accepting help 3. Education on role of caregiver in palliative care context 4. Strategies to respond to care recipient physical symptoms and emotional issues 5. Goal setting and problem solving 6. Advance care planning	1. Education regarding care recipient medications, administration, and side effects 2. Discuss importance of follow-up with primary care, specialty providers 3. Education regarding indications of changes in care recipient condition and how to respond 4. Follow-up visit/Reconnect to primary care provider 5. Integrated care plan with health & community services 6. Communicating with healthcare providers	
Timeframe of Activities		
Each Hospital Day	Post-Discharge/Community based Visits	
APN daily interaction including transition planning with FCG	Weeks 1-4 Minimum of 2 virtual visits/week by APN with FCG, phone calls as needed	Weeks 5-8 Minimum of 1 virtual visit/week by APN with FCG, phone calls as needed

access to all baseline data collected to assist with assessment and care planning (See Table 1 below for variables and measures). During the pre-discharge visits the nurse will: (1) assess the FCG's physical and emotional self-care needs, including the involvement of secondary caregivers and/or formal service providers to support the FCG and develop a FCG wellness plan; (2) assess the FCG's knowledge and skills for skillful caregiving; (3) begin transitional care planning by working with the FCG, the palliative care consulting service and acute care staff, and local community service providers; and (4) develop individualized FCG Readiness Plans (adapted from Hospice & Palliative Nurses Association and AARP materials)^{2,117} to anticipate caregiving needs that may arise when they return home. On the day of care recipient's discharge, the nurse will confirm the FCG's understanding of caregiving needs, physical and emotional readiness for caregiving, and confirm that plans for FCG self-care and respite are in place.

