Aim 3: Examine the effect of technology-enhanced TPC for FCGs on healthcare costs. The Ambulatory and Home Care Record (AHCR) will be used as our healthcare cost measure. The AHCR is designed to capture costs from a societal perspective, implying that costs from all stakeholders (FCG, care recipients, and health systems) will be collected. Developed for the Canadian health system where healthcare is primarily publicly funded,¹ the AHCR will be modified for our study to collect expenditures paid for by any type of payer (e.g., commercial, government, or other insurance; and self-pay/no insurance) instead of simply publicly-financed expenditures as in the original AHCR. Third party insurance refers to any supplemental insurance over and above the primary insurance that the patient has (see Table 2). Thus, the proposed change to the original AHCR measure is only to increase clarity regarding funders and therefore we do not anticipate any threat to the AHCR's validity. The AHCR captures self-reported utilization and cost information for care provided by all FCGs and other unpaid caregivers, paid care received at home (e.g., home health care) and outside of the home (e.g., doctor/therapy appointments), as well as medications, supplies, and equipment. Out-of-pocket costs refer to all care-related expenses not paid for by the insurance. These data will be collected monthly for 6 months following each care recipient's discharge from the index hospitalization to minimize recall bias and to account for any time lag in billing systems. The FCGs will be prompted to have all bills received during the preceding month available during the monthly AHCR data collection. Agreement between care recipients' reports on the AHCR and administrative data range from moderate ($\kappa=0.41$; 95 percent confidence interval, 0.16–0.61) for physician visits to perfect ($\kappa=1.0$) for physical therapy visits.²⁵

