We will report these measures, per subject, every month to minimize the impact of patients dying in the earlier part of the intervention interval. The difference in costs of readmissions and ED visits between the intervention and control patients will provide an estimate of the costs avoided due to the proposed intervention. We anticipate that some care recipients will die before 6 months and therefore we will need to address right censoring of utilization and costs due to patients dying before the end of the study. Accordingly, we will adopt appropriate econometric methods as described in the **Analytical Plan section below** to account for the possible censoring of utilizations and costs.

The time costs refer to the FCGs' time and, if the FCG is employed, the employer time lost in the course of

Table 2: Modified Framework for Assessment of Palliative Care Costs¹		
Expenditure Category	Privately-incurred Costs	Time Costs
Third party-incurred Costs (Commercial/ Medicare/ Medicaid/ Other/ No Insurance)		
3rd Party Insurance Reimbursement (Yes/No)	Out-of-Pocket	Caregiver lost time from
• Home-based services	• Home-based services	• Labor Market
• Ambulatory appointments	• Ambulatory appointments	• Household work
• Hospitalization	• Hospitalization	• Leisure
• Emergency Department Visits	• Emergency Department Visits	
• Facility care	• Facility care	
• Medications	• Medications	Employer Time Loss
• Supplies and Equipment	• Supplies and Equipment	
	• Paid house work	
	• Travel expenses	
Total 3rd party Expenditures	Total Out-of-Pocket Expenditures	Total Time Cost

providing care to the care recipient. Time costs for the FCGs will be valued by a human capital approach.¹⁸⁰ The most recently available data on current earnings by age and sex from the Bureau of Labor Statistics (BLS) will be used to impute the market value of time withdrawn from leisure and household work. In order to value lost time from the labor market, age- and sex-based earnings from the BLS will be adjusted for employer-paid benefits, vacations days and holidays.

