For those FCGs who are not employed outside the home, their time lost from household work will be imputed at the hourly earnings rate for the “personal care and service occupations” category in the BLS. Thus, the proposed valuation of the lost time will be a function of whether the time is diverted from the labor market, household work, or leisure. Dr. [REDACTED] (Co-I) will lead all aspects of this Aim.

Analytical Plan

Assessment of possible imbalances in the baseline covariates that may occur between the two groups, due to randomized intervention assignment, will be made by comparing the baseline characteristics between the two groups. Categorical variables will be compared using a Chi-square test or Fisher’s exact test; continuous variables will be compared using a two-sample t-test or the Wilcoxon rank sum test, as appropriate. All analyses will be 2-sided with an alpha level of $P<.01$ for significance to account for multiple comparisons and endpoints. The intent to treat analysis will serve as the principle analysis set for efficacy assessments.

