- Set realistic interim goals for achieving preferences
- Assure FCG understanding of prescribed instructions/therapies
- Promote FCG adaptation by focusing on coaching, education, problem solving, and enlisting support of family/friends in Education
 - maintenance of health and well-being and safety measures
 - teach strategies to maximize self-care
 - enlist support of family/friends/agencies to compensate for FCG time or functional deficiencies to provide care
 - counsel on need for consistent self-care activities to maintain health, well-being
- Teach and build caregiver skills in navigating health system to meet needs
 - understand meaning of symptoms
 - understand roles and responsibilities of various formal providers of care
- Teach communication skills
 - strategies to communicate effectively with healthcare providers and gain access to care when needed
 - clarification of goals/preferences of care and consequences of decisions
- Assist with resources for ethical and legal aspects of care
 - discuss advance care planning
 - assure patient treatment goals are transferable and applicable across care settings
- Psychosocial Guidance and Support for FCG
 - Promote mental health:
 - establish strategies to manage anxiety, depression
 - establish strategies to address psychological reactions of patient/FCG/family (stress and coping)
 - provide education and guidance to enhance FCG coping skills for responding to patient problems such as problem behaviors, anger, depression
 - Provide support for anticipatory grief
 - Grief plan
 - Foster quality of relationships and support systems
 - support spirituality
 - patient story – sense making
 - **Promote use of Readiness Plans related to FCG self-care**
 - Help caregiver connect with a community resources, support group as appropriate – face to face or on-line
 - Reduce amount of caregiving: encourage/arrange respite – in home, day care, institutional for holidays, temporary illness of caregiver, other demands
 - Advance care planning – goals of care

References:

Grady, P. A. and M. Gullatte (2014). "The 2014 National Nursing Research Roundtable: The science of caregiving." *Nurs Outlook* 62(5): 362-365.

Schulz, R. (2013). "Research priorities in geriatric palliative care: informal caregiving." *Journal of Palliative Medicine* 16(9): 1008-1012.

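### Aim 3 records care by other unpaid helpers but prices only the enrolled caregiver's time, so unpaid hours passed to relatives or friends could appear as a societal saving

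*Combined protocol and SAP*

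**What the plan says.** All references are to the combined protocol and SAP.

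**What is collected.** Under Variables and Their Measurements, Aim 3, the AHCR "captures self-reported utilization and cost information for care provided by all FCGs and other unpaid caregivers". Other unpaid helpers are thus named separately from FCGs. Under Sample – Target population, an FCG is the self-identified primary informal caregiver.

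**What is priced.** The text around Table 2 sets the scope: "The time costs refer to the FCGs' time and, if the FCG is employed, the employer time lost in the course of" caring for the recipient. Three valuation statements follow:
- "Time costs for the FCGs will be valued by a human capital approach".
- "The most recently available data on current earnings by age and sex from the Bureau of Labor Statistics (BLS) will be used" to value leisure and household time. Labor-market time uses the same kind of earnings data with adjustments.
- "For those FCGs who are not employed outside the home, their time lost from household work will be imputed" at a BLS rate for personal care and service occupations.

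The time column of Table 2 is headed "Caregiver lost time from" and lists labor market, household work and leisure, then employer time loss. It has no line for other unpaid helpers.

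**What the intervention does.** In Part 1 (pre-discharge), the nurse assesses the FCG's self-care needs, "including the involvement of secondary caregivers and/or formal service providers to support the FCG". Appendix A, under Teaching, Counseling and Guidance, tells the nurse to "enlist support of family/friends/agencies to compensate for FCG time or functional deficiencies to provide care". Figure 2 lists accepting help among the self-care objectives.

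**How it is used.** The Analytical Plan takes the between-arm difference in overall cost as the estimate of the model's cost impact. Aim 3 hypothesises a net societal decrease over 6 months.

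**The concern.** From a societal perspective, an hour of unpaid care that passes from the enrolled caregiver to a sibling or neighbour is still an hour of someone's time. If only the enrolled caregiver's hours carry a price, that hour drops out of the total although the care is still being given.

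The arms are not alike in this respect. Seeking help from family and friends is part of what the intervention teaches, whereas control FCGs receive reminder calls and usual care. Any omission would therefore probably be larger in the intervention arm, which favours the hypothesised saving. At stake is the interpretation of the Aim 3 overall-cost contrast. The primary endpoint and the sample size rest on Aims 1 and 2 and are unaffected.

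**Working it through.** The plan gives no figure of its own to reproduce here. The check compares the rules and then illustrates the scale.

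**1. Collection against valuation**

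| Type of care hour | Recorded in the AHCR? | Valuation rule stated? |
|---|---|---|
| FCG, labor market, household or leisure | Yes | Yes |
| FCG's employer | Listed in Table 2 | Named in the time-cost definition |
| Paid home services, facility care, paid house work | Yes | Yes, as costs in Table 2 |
| Other unpaid helpers | Yes | None |

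The age-and-sex earnings rule needs the helper's age and sex. The text describes collection of such characteristics only for participants. The AHCR form belongs to Appendix B, which was not available for this check, so what it records about helpers is unknown.

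**2. The omitted term**

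Let F and H be mean unpaid hours of the FCG and of other unpaid helpers, with subscripts I and C for the intervention and control arms, and let w and v be the respective hourly values.

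- Time-cost difference under the written rule: w(F_I − F_C).
- Societal time-cost difference: w(F_I − F_C) + v(H_I − H_C).
- Omitted: v(H_I − H_C).

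The omission flatters the intervention when H_I exceeds H_C. If an hour simply changes hands and v = w, the true difference from that hour is zero, but the written rule shows a saving of w.

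**3. Illustration of scale**

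Neither the hours moved nor their value is in the documents. Assumed: 2, 5 or 10 hours per week (intervention minus control) at $12 to $25 per hour. Two durations are used: the 8 weeks of the intervention, and 26 weeks for the 6-month cost period. Omitted cost per dyad = hours per week × weeks × rate.

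| Hours/week and rate | 8 weeks | 26 weeks |
|---|---|---|
| 2 at $12 | 2×8×12 = $192 | 2×26×12 = $624 |
| 5 at $15 | 5×8×15 = $600 | 5×26×15 = $1,950 |
| 5 at $20 | 5×8×20 = $800 | 5×26×20 = $2,600 |
| 10 at $25 | 10×8×25 = $2,000 | 10×26×25 = $6,500 |

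The 26-week column assumes that the shift outlasts the intervention and that the recipient is alive throughout. The plan expects some deaths before 6 months.

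**The case against.** The strongest reply is that nothing says helpers' hours will be discarded. The AHCR gathers them, and the heading "Caregiver lost time from" in Table 2 is generic enough to admit them. A reader might infer that the plan has deliberately excluded them; the documents do not support that. They show a mismatch between what is collected and what is valued. Still, the defining sentence limits time costs to FCGs and employers, and a generic column heading does not supply a pricing rule.

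Second, the intervention text is not only about unpaid helpers. The Appendix A instruction also names agencies, and the respite it encourages includes day care and institutional care. Insofar as these are paid for, Table 2 costs them. This stands: only hours moved to unpaid helpers are at issue, and the documents do not show that to be the main route.

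Third, the direction is not guaranteed. The intervention also teaches hands-on care and takes up FCG time in visits, and control FCGs may enlist relatives too. This also stands, and is why the arm difference is called probable.

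Fourth, the Analytical Plan reports cost components individually and FCG cost separately. That would reveal a fall in FCG cost, but not whether helpers' hours rose to match it, and it would not bring those hours into the total.

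**Conclusion.** The point holds as a mismatch. The AHCR captures care by other unpaid caregivers, but the written definition and pricing rules cover only the FCG's time plus employer time. Applied literally, unpaid hours passed to other helpers leave Total Time Cost and appear as a societal saving, probably more often in the intervention arm.

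The size cannot be derived from the documents. Under the assumed hours and rates it is $192-$2,000 per dyad over 8 weeks and $624-$6,500 over 26 weeks. A reader might be tempted to express this as a percentage of the $2,000 per month in Sample Size and Power Calculations. That would mislead: the $2,000 is a healthcare cost, while the total affected also contains time costs, so the share would be overstated. Nor does every moved hour have to be wholly spurious, because the plan lets the value of time depend on what it is withdrawn from.

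The plan should be changed before analysis. Otherwise the treatment of helpers' hours would be settled with the data in view.

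**What to change.** In the Aim 3 time-cost text and Table 2:

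- Define Total Time Cost as the hours of all unpaid caregivers recorded in the AHCR.
- Price other helpers' hours at the BLS personal care and service occupations rate, which the plan already names for non-employed FCGs, unless the AHCR records what the age-and-sex rule needs.
- Show FCG time as a separate sub-line, so that the caregiver's own burden and the societal total can both be read.
- Add a line for other unpaid helpers to the participant worksheet, which the Analytical Plan models on Table 2.

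The cost is SAP wording, one extra worksheet line and one extra sum, provided that the AHCR form records helpers' hours in usable form; this should be confirmed against Appendix B. The drawback is precision: helpers' hours are reported by the FCG as proxy and will be noisier than the FCG's own.

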Upon completion of the informed consent process, the SC will retain documentation of the FCG's consent and the care recipient's consent/assent along with the assessment in the research study files, including the name and job title of the study team member who explained the study, a brief description of what was explained, questions (if any) that were asked and answered, confirmation that the subject expressed understanding of the study and willingness to participate, and the list of written information given to the subject.

Based on recruitment approaches, including introduction of the study by our trained SC and, when possible, by the members of the hospital palliative care consulting service, review of palliative care admission lists by a study coordinator, FCG remuneration, our prior experience enrolling hospice eligible patients while still hospitalized,¹⁴⁶ and flexibility in data collection to meet FCG preferences, we are confident in our ability to recruit the necessary 8 participants per month to meet the subject accrual goals in a timely manner.

Sample Size and Power Calculations

Determination of sample size is based on the analyses of study Aims 1 and 2 to detect a meaningful effect size. The focus of this study is FCGs. With a sample size of 100 FCGs per group, we will have 80% power to detect an effect size 0.487 at an alpha level of 0.01, assuming a two-sided, two-sample t-test is appropriate. This suggests that if a standard deviation of difference between two groups for a particular endpoint is 1 unit, then a difference of 0.487 points per month between two groups for that endpoint will be detectable with this sample size. Given that our primary outcome of interest is rate of change, only FCGs with at least one post-baseline measurement would be able to be evaluated. To account for a possible attrition rate of ~30%,⁹ due to unanticipated events such as loss to follow-up, we plan to recruit a total of 500 FCGs per group at an average of 8 FCGs per month over a planned 36-month enrollment period. We are confident we will enroll the target number of FCGs, as there were over 300 patients seen by the palliative care consulting service in both 2014 and in 2015 and discharged home to the major catchment area of the study setting.

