Aims 1 and 2. Statistical analyses of Aims 1 and 2 will be performed in a similar manner. Every FCG will be evaluated using various scales and survey instruments at baseline, 2 weeks, and 8 weeks post patient discharge (Table 1). We will use a response-feature analysis as our primary approach in analyzing these repeated measures data.¹⁸¹ For each FCG, the magnitude of the scores from the respective instruments will be plotted versus time (measured in months); least squares regression will be used to estimate a participant-specific rate of increase in points per month. This slope parameter estimate will be used as the response feature for each participant and is the primary endpoint for this study. The primary analysis of this endpoint will be analyzed using a two-sample t-test or Wilcoxon rank-sum test, as appropriate. The endpoints will also be analyzed using a fixed-effects linear regression model. This model will use the estimated regression-slope response-feature as the dependent variable and have independent variables consisting of intervention (yes, no) as well as any baseline covariates such as FCGs’ age, employment status, etc. These analyses will adjust for any possible imbalances in these baseline covariates among FCGs that occur due to the randomized assignment to the intervention. This analysis approach will hold for those endpoints collected only at two time points (i.e., baseline and 8 weeks).

Aim 3. Descriptive statistics, including mean, median, and standard deviation (minimum and maximum) for the utilization measures (i.e., hospitalizations and ED visits) will be provided. Considering the count nature of the utilizations, and to also account for any potential differences between the baseline characteristics of the care recipients in the two study arms, we will use Poisson regression to model various utilization outcomes.¹⁸² We expect that the gains (decreased healthcare utilization and costs) will be sustained beyond the enrollment period. Therefore, both descriptive and multivariable-adjusted measures will be estimated for the intervention period and the subsequent months post-intervention. A limitation of this economic approach will be the memory recall of the FCGs. We will provide a worksheet similar to Table 2 for all participants to help them track services and costs.

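### The analysis set is called intention to treat, but the slope endpoint makes it an available-case (modified ITT) set, and Aims 1 and 2 have no protection against selective loss to follow-up

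*Combined protocol and SAP*

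**What the plan says.** The Analytical Plan names the principal set for efficacy: "The intent to treat analysis will serve as the principle analysis set for efficacy assessments". It does not define that set further.

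Under Aims 1 and 2 the schedule is: "Every FCG will be evaluated using various scales and survey instruments at baseline, 2 weeks, and 8 weeks post patient discharge". A least-squares line is fitted to each caregiver's scores, and "This slope parameter estimate will be used as the response feature for each participant and is the primary endpoint for this study". On the test: "The primary analysis of this endpoint will be analyzed using a two-sample t-test or Wilcoxon rank-sum test, as appropriate". A supporting regression uses the same slopes as its dependent variable, with arm and baseline covariates such as age and employment status. The baseline score of the instrument is not named among them. Slopes from two scores are accepted: "This analysis approach will hold for those endpoints collected only at two time points".

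Sample Size and Power Calculations says that "only FCGs with at least one post-baseline measurement would be able to be evaluated", and the next sentence allows for possible attrition of about 30%. The power statement is: "With a sample size of 100 FCGs per group, we will have 80% power to detect an effect size 0.487". It rests on a t-test with both tails at the 0.01 level.

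A method for incomplete follow-up (censored regression) is given for Aim 3 only. For Aims 1 and 2 there is no imputation, no likelihood-based repeated-measures model and no missing-data sensitivity analysis.

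**The concern.** A caregiver with a baseline score and nothing afterwards has no slope. That caregiver was randomized but leaves the principal analysis because of something that happened after randomization. The supporting regression cannot bring the caregiver back, because it models the same slopes.

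If those who leave differ from those who stay, and differ in a way that depends on arm, the comparison of slopes is biased on any Aim 1 or 2 endpoint affected. The plan gives grounds to take this seriously. It describes caregivers as burdened and prone to depression. It concedes that data may be hard to obtain from a caregiver after a death. Contact also differs sharply by arm: repeated nurse video visits against a reminder call. The plan offers no way to see how far such loss could move the result, and a reader of the eventual report would take the ITT label as assurance on this point.

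There is a second, smaller matter. A caregiver seen only at baseline and 2 weeks stays in, but with a very imprecise slope that the t-test weights like any other.

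**Working it through.** **1. The plan's power figure.** Inputs from Sample Size and Power Calculations: 100 per group, effect 0.487 SD, two-sided alpha 0.01. The noncentral t calculation (198 degrees of freedom, noncentrality 0.487 × √(100/2) = 3.44) gives 79.9%; the stated 80% reproduces.

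**2. How many may be lost.** 100/(1 − 0.30) = 143 per group. Accrual of 8 × 36 = 288 is 144 per group, and 144 × 0.70 = 100.8. So 100 per group is the evaluable number, and 0.30 × 288 = 86 randomized caregivers are budgeted as not evaluable. The stated target of 500 per group does not fit this accrual; that is a separate issue.

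**3. Unequal precision.** Assume independent errors of equal variance and baseline at week 0. The error variance of a slope is proportional to 1/Σ(t − t̄)².
- Weeks 0, 2, 8: Σ = 11.11 + 1.78 + 21.78 = 34.67
- Weeks 0, 8: Σ = 32; ratio 34.67/32 = 1.08
- Weeks 0, 2: Σ = 2; ratio 34.67/2 = 17.3

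**4. Illustration: equal loss rates, different pattern by arm.** Assumptions, none from the documents except the 30%: 30% lost in each arm; intervention-arm dropouts average 0.5 SD (range 0.3 to 0.8) more distressed at baseline than their arm's mean; control dropouts random; baseline-to-week-8 correlation 0.5; the 0.487 is read as SDs of change.
- Baseline shift in retained intervention caregivers: (0.3/0.7) × 0.5 = 0.214 SD, towards less distress
- Bias by regression to the mean: (1 − 0.5) × 0.214 = 0.107 SD
- SD of change: √(2 × (1 − 0.5)) = 1, so the bias is on the scale of the 0.487; 0.107/0.487 = 22%
- Direction: retained intervention caregivers drift back towards the mean, so the bias is against the intervention

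With 100 per group at alpha 0.01:

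| Assumed baseline gap | Bias (SD) | Power if true effect is 0.487 | Rejection rate under the null |
|---|---|---|---|
| 0.3 | 0.064 | 65% | 0.018 |
| 0.5 | 0.107 | 53.5% | 0.034 |
| 0.8 | 0.171 | 36% | 0.085 |

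Of the 0.034, 0.0340 is in the harm direction and 0.0004 favours the intervention. If the 0.5 SD is instead measured against the retained caregivers, the bias is 0.5 × 0.3 × 0.5 = 0.075, power is 62% and the null rejection rate 0.021.

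A simulation of the central case under the null (143 per arm, 10,000 runs) gave a bias of 0.107 and rejection of 0.033 for the change t-test. Conditioning on the baseline score gave 0.000 and 0.011.

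**5. Illustration: different loss rates, same pattern.** Let observed and missing caregivers differ by g SD of slope in both arms. The observed mean exceeds the arm mean by g × m, where m is the fraction lost, so the bias is g × (m₁ − m₂). With 143 per group, SE = √(1/n₁ + 1/n₂), nᵢ = 143(1 − mᵢ), and g from 0.25 to 1.0:
- 30% and 30%: bias 0, type I error 0.010
- 35% and 25%: bias 0.025 to 0.10, type I error 0.011 to 0.031
- 40% and 20%: bias 0.05 to 0.20, type I error 0.015 to 0.120

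**The case against.** The strongest reply is that the plan limits the loss and keeps what matters most in ITT. Nothing excludes a caregiver for missed visits, nursing-facility placement or the care recipient's death. Variables and Their Measurements schedules collection from all caregivers, and about 2 weeks after a death. Potential Problems & Alternative Strategies adds repeated attempts, a choice of mode, alternate contacts and remuneration. The pilot reported committed caregivers. All of this stands, and it lowers the likely amount of missing data. It does not say how the remainder will be analysed.

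It is also fair that response-feature analysis is a recognised method, and that the one-arm dropout pattern in step 4 is an assumption with no support in the text. In that scenario, adding the baseline score to the regression already planned would remove the bias. That lighter change would not deal with the unequal precision of the slopes.

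A reader might infer three stronger things that the documents do not support:
- **That this is a completer analysis.** One post-baseline score suffices, so a caregiver lost after week 2 stays in.
- **That ITT gives no protection at all.** Analysis as randomized is intact; the gap is selective loss to follow-up.
- **That 30% will certainly be excluded.** The figure is a possible attrition rate. Reading it as the share with no post-baseline score is an inference from the adjacent sentence and the sample-size inflation, and is best treated as an upper planning figure.

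**Conclusion.** The point holds as a mislabelled analysis set and a missing safeguard. The primary set is available-case, with up to about 30% of randomized caregivers (some 86 of 288) allowed for as not evaluable. Aims 1 and 2 have no method or sensitivity analysis for that loss, and slopes that can differ about 17-fold in error variance count equally. The 17-fold figure assumes independent errors and concerns error variance alone; genuine between-caregiver variation in slope would narrow the ratio of total variances.

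The size of any bias cannot be read from the documents. It needs loss that is related to outcome and that differs between arms in rate or pattern. Under the step 4 assumptions it is about 0.11 SD (0.06 to 0.17) against the intervention. The main cost there is power, and the 0.034 null rejection rate should not be read as a raised chance of a false efficacy claim. With the same loss rate and pattern in both arms, there is no bias under the null. The change is worth making because it is cheap, not because bias has been shown.

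**What to change.** In the Analytical Plan, including the text for Aims 1 and 2:

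1. Define the principal set as all randomized caregivers, analysed as randomized. Make the primary analysis a linear mixed model on all their observed scores, with a common baseline mean across arms and the arm-by-time contrast in points per month. This keeps the effect measure, uses the baseline scores of those lost later, and gives less weight to caregivers seen only early.
2. Keep the slope t-test (or rank-sum test) as a sensitivity analysis labelled as restricted to caregivers with at least one post-baseline score.
3. Add one delta-adjusted (tipping-point) analysis, with the shift varied separately by arm.

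No new wording on continued assessment is needed, since the plan already collects outcomes from all caregivers.

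The cost is revised analysis text and modest programming, with no new data. The model assumes data missing at random, and a caregiver with only a baseline score adds no post-baseline information to it. The tipping-point analysis checks how far the conclusion depends on that assumption.
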